8.5 RECIST 1.1 and Disease Assessment

Efficacy endpoints in this study, including ORR, DoR, and PFS, will all be based on tumor assessment scan evaluation by RECIST 1.1².

RECIST assessments will be performed using contrast-enhanced CT/MRI assessments of chest, abdomen, and pelvis. Additionally, x-ray and bone scans will be used as appropriate. Additional

BerGenBio ASA
[name]
[name]
Norway

anatomy should be imaged based on signs and symptoms of individual patients at baseline and follow-up. Baseline assessments should be performed no more than 28 days before start of study treatment, and ideally should be performed as close as possible to the start of study treatment.

All radiological and non-radiological (e.g., MRI) scans will be reviewed by the local site investigator; and if possible, stored electronically (de-identified with the patient's notes) at site.

A maximum of 5 target lesions, maximum of 2 per organ, must be selected at baseline. All target lesions are measurable. Target lesions should be selected on the basis of their size (longest diameter for non-nodal lesions or short axis for nodal lesions), but in addition should be those that lend themselves to reproducible repeated measurements.

All remaining lesions present at baseline are considered non target, irrespective of whether they are measurable.

Disease assessments will be performed every 9 weeks \pm 7 days for the first 46 weeks relative to the date of first treatment administration and then every 12 weeks \pm 7 days thereafter until confirmed objective disease progression as defined by RECIST 1.1² (irrespective of the reason for stopping treatment or subsequent therapy).

Any other sites at which new disease is suspected should also be adequately imaged at follow-up.

If an unscheduled assessment was performed and the patient has not progressed, every attempt should be made to perform the subsequent assessments at their scheduled visits. This schedule is to be followed in order to minimize any unintentional bias caused by some patients being assessed at a different frequency than other patients.

Table 20 provides the RECIST 1.1² evaluation and definitions of disease response (based on target lesions (TL)):

Table 20: RECIST 1.1 Evaluation and Definitions of Disease Response

Complete Response (CR)	Disappearance of all TLs since baseline. Any pathological lymph nodes selected as TLs must have a reduction in short axis to <10 mm.
Partial Response (PR)	At least a 30% decrease in the sum of the diameters of TLs, taking as reference the baseline sum of diameters
Stable Disease (SD)	Neither sufficient shrinkage to qualify for PR nor sufficient increase to qualify for PD
Progression of disease (PD)	At least a 20% increase in the sum of diameters of TLs and an absolute increase of at least 5 mm, taking as reference the smallest sum on study (this includes the baseline sum if that is the smallest on study).
Not Evaluable (NE)	Only relevant if any of the TLs were not assessed or not evaluable or had a lesion intervention at this visit. Note: if the sum of diameters meets the progressive disease criteria, progressive disease overrides not evaluable as a TL response

The objective response must be confirmed by a repeat scan performed at least 4 weeks later.

Details of any new lesions will also be recorded with the date of assessment. The presence of one or more new lesions is assessed as progression, however, in the absence of clinical deterioration, treatment can continue. The suspected disease progression should be confirmed after 28 days.

A lesion identified at a follow up assessment in an anatomical location that was not scanned at baseline is considered a new lesion and will indicate disease progression.

BerGenBio ASA
[name]
[name]
Norway

The finding of a new lesion should be unequivocal: i.e., not attributable to differences in scanning technique, change in imaging modality, or findings thought to represent something other than tumor.

If a new lesion is equivocal, for example because of its small size, the treatment and tumor assessments should be continued until the new lesion has been confirmed. If repeat scans confirm there is a new lesion, then the progression date should be declared using the date of the initial scan. Disease progression requires confirmation. The confirmatory scan should occur preferably at the next scheduled visit and no earlier than 4 weeks after the initial assessment of progression of disease (PD) in the absence of clinical deterioration.

The overall visit response will be derived using the algorithm shown in [Table 21](#):

Table 21: Overall Visit Response Algorithm

Target Lesions	Non-Target Lesions	New Lesions	Overall Response
CR	CR	No or NE	CR
CR	NA	No or NE	CR
CR	Non-CR/Non-PD	No or NE	PR
CR	NE	No or NE	PR
PR	Non-PD or NE or NA	No or NE	PR
SD	Non-PD or NE or NA	No or NE	SD
NE	Non-PD or NE or NA	No or NE	NE
PD	Any	Yes or No	PD
Any	PD	Yes or No	PD
Any	Any	Yes	PD

CR Complete response, PR Partial response, SD Stable disease, PD Progression of disease, NE Not evaluable, NA Not applicable (only relevant if there were no non-target lesions at baseline).

8.5.1 Immune-related RECIST and confirmation of progression

RECIST 1.1² will be adapted to account for the unique tumor response characteristics seen with treatment of pembrolizumab. Immunotherapeutic agents such as pembrolizumab may produce antitumor effects by potentiating endogenous cancer-specific immune responses. The response patterns seen with such an approach may extend beyond the typical time course of responses seen with cytotoxic agents and can manifest a clinical response after an initial increase in tumor burden or even the appearance of new lesions. Standard RECIST may not provide an accurate response assessment of immunotherapeutic agents such as pembrolizumab. Therefore, RECIST 1.1² will be used with the following adaptations:

If radiologic (or non-radiological) scan suggests that the patient has progressive disease (initial PD), tumor assessment should be repeated ≥ 4 weeks later in order to confirm PD with the option of continuing treatment per below while awaiting radiologic confirmation of progression.

- If repeat scan shows $<20\%$ tumor burden compared to nadir, stable or improved previous new lesion (if identified as cause for initial PD), and stable/improved non-target disease (if identified as cause for initial PD), treatment may be continued / resumed.
- If repeat scan confirms PD due to any of the scenarios listed below, patients will be discontinued from study therapy.

BerGenBio ASA
[name]
[name]
Norway

In determining whether the tumor burden has increased or decreased, site study team should consider all target lesions as well as non-target lesions.

Scenarios where PD is confirmed at repeat scan:

- Tumor burden remains $\geq 20\%$ and at least 5 mm absolute increase compared to nadir;
- Non-target disease resulting in initial PD is worse (qualitative);
- New lesion resulting in initial PD is worse (qualitative);
- Additional new lesion(s) since last evaluation.

In patients who have shown radiological PD, it is at the discretion of the treating physician whether to continue a patient on study treatment until a repeat scan is obtained. When feasible, patients should not be discontinued from their study treatment until progression is confirmed. When clinically stable, patients may continue pembrolizumab beyond RECIST 1.1² progression with continued assessment of response. iRECIST reflects that some patients can have a transient tumor flare after the start of immunotherapy, but with subsequent disease response. Patients that are deemed clinically unstable are not required to have repeat scan for confirmation of progressive disease and best medical practice is to be applied. For the purpose of this decision process, lack of clinical stability is defined as:

- Unacceptable toxicity
- Clinical signs or symptoms indicating clinically significant disease progression
- Decline in performance status
- Rapid disease progression or threat to vital organs or critical anatomical sites (e.g., CNS metastasis, respiratory failure due to tumor compression, spinal cord compression) requiring urgent alternative medical intervention.

8.6 Completion and Closure of the Study

The study will be completed when either:

- The DRC recommends early termination following the review of the ORR and risk-benefit at
 - the interim (Stage 1) analysis of cohort A or
 - the interim (Stage 1) analysis of cohort B or
 - the interim (Stage 1) analysis of cohort C.

Or

- Once all patients have been followed up for at least 24 months (i.e., LPLV) (unless the patients have died or withdrawn from the study due to other reasons before this time). At this point, the database lock will occur and final analyses will be performed (study completion) and the results will be reported in the final CSR.

At the time of study completion there may be patients continuing on study treatment, any remaining patients continuing to show benefit from the study treatment will be offered access to bemcentinib (e.g., under expanded access program or roll over study) outside the study, after discussion with the sponsor, prior to study closure.

BerGenBio ASA
[name]
[name]
Norway

For patients ongoing on the study treatment beyond study closure, only limited data will be collected. An addendum (or addenda) to the CSRs will be generated to report any outstanding safety data.

Study start is defined by the first patient to enter screening, however, the First Patient In (FPI) is when the first patient receives the first dose of study drug.

Last Patient In (LPI) is the last (EE) evaluable patient enrolled in the study (C1D1).

LPLV is defined as the last visit of the last evaluable patient (EE) enrolled in the study (i.e., when all the enrolled patients have been followed for at least 24 months).

Study completion is defined by the date of LPLV and includes all data for the final analysis of all evaluable patients (EE).

Study closure is defined by study completion, when all patients have completed their study visits and have been withdrawn from the study and the CSR has been produced (excluding any CSR addendum for safety data).

8.7 Demographic, Medical History, Prior Medication and Other Baseline Characteristics

Demographic characteristics, medical history, prior medication and other baseline data will be listed and summarized using descriptive statistics for continuation data and contingency tables for categorical data. Prior medication will be summarized by Anatomical Therapeutic Chemical (ATC) terms.

8.8 Study Treatment

The number of doses of bemcentinib and pembrolizumab by cycle and over entire study period will be listed and summarized using descriptive statistics. The time on study drug until last treatment received will be listed and presented by descriptive statistics.

8.9 Concomitant Medication

Concomitant medication and significant non-drug therapies after the start of study treatment will be listed and summarized by ATC term in contingency tables.

8.10 Reasons for Discontinuation from Study Treatment

Reasons for discontinuation of study treatment will be listed and summarized.

8.12 Secondary Objectives

8.12.1 Safety

8.12.1.1 Adverse events

Adverse events will be coded as described in [Section 8.4](#). The number of AEs occurring at least once in a patient will be listed and summarized by contingency tables for:

- primary system organ class, preferred term;
- preferred term;
- NCI CTCAE grade;
- relationship to both study drugs;
- interruption of study drug;
- leading to discontinuation;
- Grade 3 and higher;
- SAEs;
- AEs leading to death;

BerGenBio ASA
[name]
[name]
Norway

- standard medical queries

8.12.1.2 Safety laboratory

Laboratory values will be graded by NCI CTCAE version 5.0, if no grading exists values will be classified into low/normal/high based on laboratory normal ranges. Each parameter will be presented by descriptive statistics at each visit and change from baseline values at each visit. Shift tables for CTCAE grades and normal ranges will be presented. All laboratory values will be listed. A separate listing for abnormal lab values (Grade 3 and higher, and low/high values) will be presented.

8.12.1.3 Vital signs

Vital signs will be summarized by descriptive statistics at each visit, change from baseline will be presented and a listing will be provided.

8.12.1.4 Electrocardiogram

ECG data will be listed overall and a separate listing for any clinically significant finding in ECG values will be provided.

8.12.2 Efficacy

8.12.2.1 Duration of response

The DoR will only be calculated for patients that have an objective response. The duration of response is calculated from the date of the first documented response until the date of progression or death; patients who continue to respond at the date of data cut-off (LPLV) will be censored using the same date used to censor for the PFS time. Median DoR and respective 95% CIs will be presented.

8.12.2.2 Disease control rate

Disease control rate (DCR) is defined as the percentage of patients with a PR, CR or with stable disease (out of number EE evaluable). A 95% CI for the DCR will be calculated using an exact binomial distribution.

A Kaplan Meier plot of the duration of response will be presented along with the median duration of response. Descriptive statistics will be used as required, including 95% CIs.

8.12.2.3 Progression free survival and overall survival

Kaplan Meier plots of the time to progression and death will be presented, along with the median progression free survival (PFS), median overall survival (mOS), and overall survival (OS), as well as the estimated survival at 12 months. Descriptive statistics will be used as required, including 95% CI.

PFS is measured from the date of the 1st dose of the 1st cycle until the date of progression (the date on which the progression is initially observed) or the date of death (whichever is earlier). A sensitivity summary of PFS using the first date that a progression is considered (irrespective of whether confirmed) will additionally be conducted. Patients who have not progressed or died before the date of data cut-off (last patient, last visit) will be censored at their last clinical evaluation.

BerGenBio ASA
[name]
[name]
Norway

OS is defined as the time from the date of enrolment until the date of death (from any cause and irrespective of any subsequent anti-cancer treatment given). Patients who remain known to be alive at the date of data cut-off (LPLV) will be censored at their date last known to be alive. The estimated survival at 12 months will be read from the Kaplan Meier OS curve. Patients who are lost to follow-up will be censored at the point last known to be alive; however, if $\geq 2\%$ of patients are in this category, a sensitivity summary will be produced to illustrate the overall survival assuming the patient died at the date last known in the trial. If possible, the date of death may be recovered from publicly available sources such as death registries.

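### PFS and DoR are censored at a clinical visit rather than the last tumor scan, and no rule says whether a first progression that is never re-scanned is an event

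*Combined protocol and SAP*

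**What the plan says.** **Censoring.** Section 8.12.2.3 states that patients with neither progression nor death by the data cut-off (last patient, last visit) "will be censored at their last clinical evaluation". What counts as a clinical evaluation is not defined. Section 8.12.2.1 says that patients still responding at cut-off "will be censored using the same date used to censor for the PFS time". Sections 5.3.10 and 8.5 both state that ORR, DoR and PFS rest on tumor scans read by RECIST 1.1.

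**Events.** The main PFS event in Section 8.12.2.3 is death, or progression dated to when it was first seen. The definition does not contain the word confirmed. The next sentence reads: "A sensitivity summary of PFS using the first date that a progression is considered (irrespective of whether confirmed) will additionally be conducted".

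**Confirmation.** Section 8.5: "Disease progression requires confirmation". The sentence after it describes the confirmatory scan as applying where there is no clinical deterioration. For a new lesion: "If repeat scans confirm there is a new lesion, then the progression date should be declared using the date of the initial scan". Section 8.5.1: "Patients that are deemed clinically unstable are not required to have repeat scan for confirmation of progressive disease".

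**Other PFS events.** Section 6.10 treats palliative radiotherapy as clinical progression for PFS and mentions no confirmation.

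**The concern.** There are two separate problems.

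1. A scan-based endpoint should be censored when progression was last ruled out by a scan. A clinic visit after that scan does not rule it out.

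2. A sensitivity summary that ignores confirmation differs from the main analysis only if the main analysis depends on confirmation in some way. If it does, the plan needs a rule for a first progression with no second scan, and it has none. This can arise in two ways: the patient is exempt as clinically unstable, or is stable but withdraws or misses the repeat scan. Section 8.12.2.3 gives OS a rule for loss to follow-up but gives PFS none.

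If a never-confirmed progression were treated as a non-event, the patient would be censored at a later visit or carried forward to death. Section 8.5.1 defines instability to include rapid progression and declining performance status. Censoring such patients would therefore be informative, and the bias would be upward.

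Median PFS and DoR are reported secondary results. In cohort A the Data Review Committee may also weigh available DoR and PFS data at the Stage 1 review (Section 8.2.2).

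**Working it through.** The plan states no PFS target, event count or power, so there is no figure to reproduce.

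**Step 1: unscanned time.** From Cycle 2, on-treatment visits are mainly 3-weekly (synopsis). Scans are 9-weekly for the first 46 weeks and 12-weekly after that (Section 5.3.10). The last 3-weekly visit before the next scan falls one scan interval minus one visit gap after the previous scan:

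- 9 − 3 = 6 weeks in the first 46 weeks;
- 12 − 3 = 9 weeks thereafter.

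That is the time that can be credited without a scan, before visit windows and missed scans.

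**Step 2: effect of the censoring date.** Exponential PFS was simulated with scans at 9, 18, 27, 36 and 45 elapsed weeks and then every 12 weeks, with 15% of events being deaths and dropout unrelated to disease. Censoring at the last 3-weekly visit instead of the last scan changed PFS by at most about 0.3 points. If dropout is linked to deterioration, this figure is not a bound.

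**Step 3: does the main PFS need confirmation?**

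- For: the sensitivity sentence; the confirmation sentence in Section 8.5; scanning continues until confirmed progression (Sections 5.3.10 and 8.5).
- Against: the main definition does not mention confirmation; Section 8.5 ties the confirmatory scan to absence of clinical deterioration; the synopsis asks for confirmation only where necessary; the exemption in Section 8.5.1 can be read as letting the progression of unstable patients stand.

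The confirmed-only reading is a fair inference but it is not stated. Under either reading, a stable patient who is never re-scanned has no rule.

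**Step 4: size if such progressions are non-events.** Bias at time t = PFS(t) with un-rescanned progressions treated as non-events − PFS(t) with every first progression counted. Assumptions not in the documents:

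- Model A: true median PFS of 17 or 26 weeks, 15% of events deaths, un-rescanned progressions censored 3 weeks later.
- Model B: 200,000 patients per scenario; median time to progression 3, 4 or 6 months; median survival after progression 8 months if re-scanned and 3 months if not; un-rescanned progressions censored one month later or carried to death; 24-month cut-off.

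The un-rescanned share is of progressions in A and of patients in B. Two base values are the 10% and 20% runs.

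| Model, median | Landmark | Handling | All counted, % | 10% not re-scanned | 20% not re-scanned |
|---|---|---|---|---|---|
| A, 17 weeks | 12 months | censored | 15.4 | 18.6 (+3.2) | 22.2 (+6.8) |
| A, 26 weeks | 12 months | censored | 29.1 | 32.8 (+3.7) | 36.6 (+7.5) |
| B, 3 months | 6.3 months | censored | 23.8 | 27.4 (+3.6) | 31.4 (+7.6) |
| B, 3 months | 6.3 months | to death | 23.8 | 27.2 (+3.4) | 30.5 (+6.7) |
| B, 4 months | 6.3 months | censored | 34.1 / 33.9 | 37.7 (+3.6) | 41.4 (+7.5) |
| B, 4 months | 6.3 months | to death | 34.1 / 33.9 | 37.2 (+3.1) | 40.1 (+6.2) |
| B, 6 months | 6.3 months | censored | 48.6 / 48.7 | 51.9 (+3.3) | 55.2 (+6.5) |
| B, 6 months | 6.3 months | to death | 48.6 / 48.7 | 51.1 (+2.5) | 53.6 (+4.9) |

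The full range is +2.5 to +3.7 points at 10% and +4.9 to +7.6 points at 20%. At 40%, Model B gives about +10 to +17 points.

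**Step 5: medians are a poor yardstick here.** In Model B with 20% not re-scanned and censored, a true median of 4 months moves the observed median from 4.1 to 6.2 months. A true median of 3 months leaves it at 4.1. The jump is one scan interval (9 × 7 / 30.4 = 2.1 months) and depends on where the curve crosses 50%. Landmark PFS is steadier, although the plan's own 12-month estimate is for OS, not PFS.

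DoR was not simulated. For DoR only the direction is argued.

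**The case against.** The strongest reply is that the plan never says unconfirmed progression is ignored. It dates progression to first observation, and exempting unstable patients most naturally means that their progression stands. Stable patients are meant to be scanned until progression is confirmed, whatever the reason for stopping treatment, so the group left over should be small. That has force. It makes the inflation conditional, but it does not supply the missing rule.

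Second, the sensitivity summary already shows any PFS gap. It does, and in these simulations, where no progression is later refuted, it coincides with the proposed main analysis. But it has no DoR counterpart and does not repair the censoring date.

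Third, Section 8.3 leaves missing data and loss to follow-up to a separate SAP. No such rules appear in the text available, and the PFS censoring date is already fixed in Section 8.12.2.3.

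Fourth, PFS is secondary and descriptive, and the decision rules rest on ORR (Section 8.1). That stands and limits the importance of the point.

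Fifth, DoR inherits the PFS censoring date for patients still responding, not an explicit confirmed-only event rule. That also stands. The upward bias in DoR depends on how progression is read there too.

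**Conclusion.** The censoring date conflicts with the scan basis of both endpoints and should be changed. Its effect is small: at most about 0.3 points of PFS under independent dropout. The event status of a first progression that is never re-scanned is undefined and should be settled before database lock. If it were a non-event, landmark PFS could be overstated by roughly 3 points at a 10% un-rescanned share and 6 to 7 points at 20%. These sizes rest on assumed medians, assumed survival after progression and an unknown un-rescanned share. They show what the ambiguity could cost and are not an estimate for this trial.

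A reader might infer that the main PFS counts only confirmed progression, censors everyone else and is therefore inflated. The documents do not support that. Confirmation in the main analysis is implied, not stated. Deaths and palliative radiotherapy already count as PFS events. The planned sensitivity summary would expose any PFS gap. The primary ORR conclusion is not affected.

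**What to change.** In Sections 8.12.2.3 and 8.12.2.1, and in the SAP, state that:

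- the first RECIST 1.1 progression is an event at its own date unless a later scan, at least 4 weeks on, shows that it was not progression;
- a progression with no repeat scan, for whatever reason, is therefore an event;
- patients without an event are censored at the last evaluable tumor assessment, or at Day 1 if there is none;
- the same event and censoring rules apply to DoR.

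Death and palliative radiotherapy stay as PFS events. The planned sensitivity summary can stay: it would still differ from the main analysis by also counting progressions that a later scan refuted.

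The cost is wording only, with no new data collection. Reported PFS and DoR may be slightly less favorable.

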
Different testing laboratories will be used for Axl kinase and PD-L1 expression.

BerGenBio ASA
[name]
[name]
Norway

The fresh (newly acquired) tumor tissue sample will be either newly obtained core needle biopsy (minimum gauge 18) or a newly obtained excisional biopsy.

The following tumor tissue alternatives are available (all options require fresh tumor tissue sample); however, if there is insufficient fresh tumor tissue available, the 3rd option below allows the submission of archival tissue in addition to the fresh tissue sample:

- Where only a core needle biopsy is used, a minimum of 4 core (with 1-cm tumor in each core) biopsy samples are required. These should be placed in formalin and processed into 2 single paraffin embedded (FFPE) blocks (2 cores in one block and 2 cores in the other block) within 24-48 hours.
- Alternatively, where only a newly obtained excisional biopsy sample is used, this biopsy should be processed into 2 paraffin embedded (FFPE) blocks within 24-48 hours.
- Alternatively, 2 core (with 1-cm tumor in each core) needle (fresh tumor) biopsies or a single newly obtained excisional biopsy sample can be submitted (processed into one FFPE block), together with either an archival (FFPE) tumor tissue block or a minimum of 10 unstained slides each 5 µm cut from the archival tumor sample block.

If archival tumor tissue blocks are to be sent, it is suggested that a minimum of 10 unstained slides each 5 µm cut from the archival tumor sample block must be sent (rather than sending the whole archival block) and clearly labelled as having come from an archival block.

The first dose of study drug must be administered within 4 weeks of commencing the Screening assessments. A tumor assessment scan by computed tomography (CT) (preferred method), or magnetic resonance imaging (MRI) of the chest, abdomen and pelvis is required during the Screening period. X-ray and bone scans can be used where appropriate (for example, for symptomatic sites that are negative on a bone scan) for disease status are required during the Screening period.

Recording of AEs and concomitant medications, plus laboratory screens including ECGs will be performed at each study visit. During Cycle 1, patients will have study visits on Days 1, 2, 3 and 4, then on Days 8 and 15. From Cycle 2 Day 1, study visits will be reduced to every 3 weeks.

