5 STUDY SCHEDULE

The study consists of a Screening period, Treatment period, Post Treatment Visit and Follow-up period. Patients will attend the clinic for Screening period assessments up to 28 days before receiving the first dose of study treatment. The Post Treatment Visit will occur 30 days (+/- 3 days) after the patient has discontinued both study treatments. All patients will continue in follow-up visits and continue to have their disease assessed and scanned (unless progression of disease has already been confirmed) and for survival status.

The study schedule will continue in keeping with the Study Assessment calendar. Patients will be required to visit the study sites for each study visit (which includes each pembrolizumab dose). From Cycle 1 Day 8 onwards, a tolerance window of +/- 3 days is permitted relative to Day 1. Pembrolizumab that cannot be given within these tolerance windows will be treated as a missed dose, although it is acceptable to have a pembrolizumab dose interruption for up to 3 weeks for reasons other than toxicity. See [Section 6.6.2](#) for details on pembrolizumab related toxicity dose interruption, including the duration of dose interruption.

It is important that the calendar schedule for tumor assessment relative to Cycle 1 day 1 is maintained (subject to permitted tolerance windows). If treatment administration is misaligned with weeks (e.g. because of treatment delay), the tumor assessment schedule should be maintained by week number ([Table 3](#), [Table 4](#), [Table 5](#) and [Table 6](#)). The schedule of disease assessment is every 12 weeks once a patient has stopped one or both or completed their (combination) treatment in the absence of progression. Assessments requiring specific timing relative to the bemcentinib or pembrolizumab dose are described in the footnotes to Schedule of Study Assessments - [Table 4](#), [Table 5](#), and [Table 6](#).

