6.5 Method of Enrolling Patient to Study Treatment

During Screening, patients will be allocated a unique screening number from RAVE once written, informed consent has been obtained. Patients will be identified by this number throughout the study. Once a Subject Number has been assigned, it cannot be used again.

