- g. Information that treatment with checkpoint inhibitors, such as pembrolizumab, and treatment with bemcentinib are associated with side effects and that the patient must inform the doctor of any side effects, even if the patient does not think they are important.
- h. An explanation that patients will continue to have 12 weekly follow-up visits (or in some cases, a telephone call) to assess their disease and/or well-being after the completion of their study treatments. Follow-up visits or telephone contact will continue until the end of the study.
- i. Information to explain that on-study blood samples will be collected for the purpose of relevant Axl signaling and inhibition biomarkers and immune profiling

The patient must give consent to participate prior to enrolment in the trial. This consent must be given in writing. The Investigator who conducts the informed consent discussion must also sign. The Investigator may delegate this responsibility to a suitably qualified member of the study team (e.g., Sub-Investigator) if permitted by local regulations. This delegation of responsibility must be recorded in the Site Study File. By giving signed consent, the patient will confirm that his or her participation is voluntary and that he or she will follow the instructions of the Investigator and answer the questions asked. Signatures must be personally dated

The signed and dated consent form(s) will be kept by the Investigator. Prior to participation in the trial, the patient should receive a copy of the signed and dated written informed consent form(s).

The consent forms must include all elements required by law, local regulations, GCP and ICH guidelines including consent to allow the Sponsor, Sponsor representative, or external regulatory auditor to review the patient's medical records. This gives permission to examine, analyze, verify, and reproduce any records and reports that are important to the evaluation of the trial.

BerGenBio ASA
[name]
[name]
Norway

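### OS runs from an undefined date of enrolment while PFS runs from first dose; any gap between the two is immortal time that raises median and 12-month OS

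*Combined protocol and SAP*

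**What the plan says.** Section 8.12.2.3 gives the two time-to-event endpoints different origins. For PFS: "PFS is measured from the date of the 1st dose of the 1st cycle until the date of progression". For OS: "OS is defined as the time from the date of enrolment until the date of death". Section 2 names median OS and 12-month OS as secondary endpoints.

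No section says which calendar date is the date of enrolment for OS. The relevant places are:

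- **Section 8.6**, in defining a study milestone: "Last Patient In (LPI) is the last (EE) evaluable patient enrolled in the study (C1D1". The same section sets First Patient In at the first dose.
- **Section 6.5**, whose heading concerns the method of enrolling to study treatment: "During Screening, patients will be allocated a unique screening number from RAVE once written, informed consent has been obtained".
- **Section 10.3**: "The patient must give consent to participate prior to enrolment in the trial", with no day attached.
- **Section 5**: "Patients will attend the clinic for Screening period assessments up to 28 days before receiving the first dose of study treatment". The synopsis sets the same limit: "The first dose of study drug must be administered within 4 weeks of commencing the Screening assessments".

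Section 8.4 restricts the efficacy set (EE) to patients with at least one dose and at least one on-treatment scan, and the safety set to patients with at least one dose.

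**The concern.** Whichever Section 8.4 set is used for OS, a patient who dies before the first dose is not in it. Time between enrolment and first dose is therefore survival guaranteed by the selection rule, and it can bias OS in one direction only, upwards. It also puts OS and PFS on different clocks: a patient who dies without progression would have an OS time longer than the PFS time by the length of the gap, for the same death.

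In a single-arm study, median and 12-month OS can be read only against outside figures, so the origin has to be explicit. As written, two programmers could defensibly use different start dates.

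**Working it through.** The plan states no OS assumption, event count or power, so there is no OS figure to reproduce. The check has three parts.

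**1. Possible length of the gap between enrolment and first dose**

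| Reading of enrolment | Gap | Basis |
|---|---|---|
| C1D1 | 0 days | Section 8.6 |
| Eligibility confirmed | about 10 days at most | Inclusion criterion 9: organ function confirmed within 10 days of treatment initiation |
| Start of screening | up to 4 × 7 = 28 days | Synopsis; Section 5 |
| Consent | no stated maximum | Consent precedes screening by an unspecified time |

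**2. Effect of a gap on OS**

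Assumptions: exponential survival from first dose with median m months; the same gap of g months for every patient; 1 month = 30.4375 days. The range m = 8 to 12 is an assumption. Section 1.1 gives 8 to 10 months, but as general Stage IV background and not as a design value.

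- The median becomes m + g.
- 12-month OS changes from S(12) = 2^(−12/m) to S(12 − g) = S(12) × 2^(g/m).

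For 28 days, g = 28/30.4375 = 0.92 month:

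| m (months) | S(12) | S(12 − g) | Difference |
|---|---|---|---|
| 8 | 35.4% | 38.3% | +2.9 points |
| 10 | 43.5% | 46.4% | +2.9 points |
| 12 | 50.0% | 52.7% | +2.7 points |

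Shorter gaps over the same medians:

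- 14 days: g = 0.46 month; +1.3 to +1.4 points.
- 10 days: g = 10/30.4375 = 0.33 month; about +1.0 point (for m = 10, 0.435 × (2^0.033 − 1) ≈ 0.010).
- 7 days: g = 0.23 month; +0.7 point.
- 0 days: no change.

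**3. What a first-dose origin leaves in place**

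OS sits under the efficacy endpoints (Section 8.12.2), and Section 8.4 assigns efficacy to the EE set. The first on-treatment scan is due 9 weeks after first dose, ± 7 days: 63 ± 7 = 56 to 70 days. A patient scanned on schedule must have survived that long to be counted, and Section 3.5 replaces patients who are not evaluable. With a full screening period in front, guaranteed survival is 56 + 28 = 84 to 70 + 28 = 98 days (2.8 to 3.2 months). Moving the origin to first dose removes the 28 days but not the 56 to 70.

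**The case against.** The strongest reply is that enrolment in this protocol already means first dose, or close to it. Section 8.6 ties the last enrolled patient to C1D1. Section 8.2.1 and the synopsis equate six weeks of follow-up after enrolment with two treatment cycles, which works only if enrolment falls at about first dose. The synopsis counts about 133 patients screened against up to 106 enrolled, so screening and enrolment are separate events. Section 10.3 places consent before enrolment, and Section 6.5 never calls allocation of the screening number enrolment. All of this stands, and it makes a gap near zero the better-supported reading. But Section 8.6 defines a milestone, not the OS origin, and Section 8.12.2.3 uses different words for PFS and OS in consecutive definitions.

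The size can also be challenged. Even the 28-day case is small beside sampling error: near 50% survival without censoring, an approximate 95% interval is ±1.96 × √(0.25/29) ≈ ±18 points for 29 patients and ±14 points for 48. OS is descriptive, with no test or threshold. That is correct and limits the importance of the point, although a one-directional bias does not average out as sampling error does.

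Finally, Section 8.3 defers detail to a separate SAP. The text available contains no further OS definition, so whether one fixes the date cannot be checked.

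**Conclusion.** The point holds as an undefined OS origin that differs in wording from the PFS origin. Any gap it permits is immortal time and raises both OS summaries. The size runs from zero, if enrolment is C1D1, to about +0.9 month on median OS and +2.7 to +2.9 points on 12-month OS, if enrolment were the start of screening and every patient used all 28 days. The upper figures rest on an assumed exponential curve and assumed medians of 8 to 12 months.

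A reader might infer that OS here does contain up to 28 days in which patients could not have died, or that Section 6.5 sets a consent-based origin. The documents do not support either: no section equates enrolment with consent or the start of screening, and the only one that attaches a study day to it names C1D1. The 28 days are an upper case under one reading, not an expected value.

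If the EE set is used for OS, the scan condition contributes more guaranteed survival than the 28-day screening window. The primary endpoint, the Simon rules and the power are untouched.

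**What to change.** In Section 8.12.2.3, define OS as the time from the date of first dose (C1D1) to death from any cause, the same origin as PFS. This costs one phrase; if C1D1 was always intended, it only records that.

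Separately, report OS in all treated patients, using the safety set as Section 8.4 defines it (at least one dose of either drug), so that deaths before the first scan are counted. This costs one additional Kaplan-Meier summary per cohort and needs no new data: Section 5 already keeps all patients in follow-up for survival status.
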